6.0 TREATMENT INFORMATION

6.1 Potential Risks of VR distraction

While this study is considered low risk, patient discomfort and motion sickness are potential risks. Should a patient experience any discomfort or motion

sickness, VR device will be removed, and the subject will be excluded from study. Disposable VR covers will be used, and device will be sanitized between patients to minimize risk of infection.

There is a risk of the loss of confidentiality, but measures will be taken to minimize this risk, such as only the named study staff will be handling the study forms and all the subjects will be assigned unique study numbers. The only document that could identify a patient is the informed consent that would be linked to a study participant by a study number. These informed consents will be kept in a locked cabinet in the locked office of the principal investigator. No other identifiers will be collected as a part of the research data that links a study number to the patient PHI.

For the safety of the researchers and patients, all mYPAS patient observations on day of CCBD visit, as well as any further consent questions, will be performed through a virtual telemedicine platform with approved tablets run and vetted by telemedicine at Children's Health System of Texas (CHST). The process has already been approved and vetted by CHST telemedicine so that there is little to no risk of virtual PHI breach.

7.0 STATISTICAL CONSIDERATIONS

7.1 Design/Study Endpoints

To assess the effect of the VR on children's Modified Yale Preoperative Anxiety Scale (mYPAS), a cross over study will be performed. Subjects will be randomized (1 to 1 randomization via Proc Plan in SAS 9.4) at their initial encounter to either VR or Non-VR. During their second visit patients will be given the alternative mode of care (i.e. patients who initially received VR distraction will be given Non-VR distraction, and patients who initially received Non-VR distraction will receive VR distraction)

7.2 Sample Size and Accrual

To fully power our study, we will recruit 77 patients to detect a difference of 3.5 in the mYPAS score; assuming a standard deviation of 10, a 10% reduction in patient participation due to attrition, and a power of 0.8. If attrition exceeds 10% additional post hoc power analysis will be performed.

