7.3 Data Analyses

Categorical outcomes will be presented as frequency and percentages and compared using chi-square and/or Fisher's exact test. Continuous outcomes will be summarized by median and inter-quartile range (IQR) OR mean and standard deviation (depending on the data's distribution). Depending on the data's distribution a paired t-test or Wilcoxon-sign rank test will be performed to assess the difference between VR distraction and Non-VR distraction. For this crossover design a mixed model will also be implemented, which accounts for

treatment/intervention (VR vs. non-VR), sequence, and period as fixed effects. Patients will be nested within sequence.

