7.4. Interim Analysis Plan

[figure not shown]
Interim Analysis for Efficacy and Safety

This two-sided symmetrical group sequential design, which is based upon the existing sample size specified in the protocol (N=77), has two planned stages: 1 interim stage at information fraction 0.67 (n=52) and a final stage (N=77). We will implement the two-sided O'Brien-Fleming methodology to monitor the clinical trial for early stopping because of efficacy or "safety" (exacerbated anxiety). The latter is not anticipated, but will be evaluated. We used the procedures of PROC SEQDESIGN in SAS to create the group sequential design by computing boundary values for the stages (based on the O'Brien-Fleming methodology). The boundary values are derived in such a way that the overall Type I (0.05) and Type II (0.20) error probability levels will be maintained in this design. With early stopping to reject the null hypothesis, the lower rejection boundary is constructed by connecting the lower critical values (on the Z scale) for the stages. Similarly, the upper rejection boundary is constructed by connecting the upper critical values (on the Z scale) for the stages. See Table 1 and Figure 1 (boundary plot).

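### The only planned response to attrition above 10% is an undefined post hoc power analysis; a committed confidence interval read against the planned 3.5 points would be more informative

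*Combined protocol and SAP*

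**What the plan says.** Section 7.2 of the combined protocol and SAP gives the target: "we will recruit 77 patients to detect a difference of 3.5 in the mYPAS score". The remaining planning inputs there are an SD of 10, 10% attrition and 80% power. The section closes with its only provision for heavier loss: "If attrition exceeds 10% additional post hoc power analysis will be performed". It does not say which effect size or SD that analysis would use, or how the answer would be read.

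Section 7.3 says that, depending on the distribution, "a paired t-test or Wilcoxon-sign rank test will be performed to assess the difference between VR distraction and Non-VR distraction". It adds a mixed model with treatment, sequence and period as fixed effects. It does not commit to an interval for the treatment difference, and it links no analysis to attrition.

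Section 7.4 sets the error rates ("overall Type I (0.05) and Type II (0.20) error probability levels will be maintained in this design") and a two-sided final boundary of ±2.004. It notes that SEQTEST is able to produce estimates, confidence limits and p-values once the trial stops. That is offered as a possibility. No interval is compared with 3.5.

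**The concern.** Attrition above 10% is a realistic prospect. Each child must come back for a second port access, and Sections 5.2 and 6.1 take children with VR discomfort or motion sickness out of the study. With fewer pairs a non-significant result becomes more likely. The reader's question is then whether the data are still compatible with the benefit the trial was sized to find. A power figure computed after the data are in does not answer that, whichever inputs go into it. What is at stake is how a null result is read, not the test itself.

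**Working it through.** **Inputs.** N = 77, difference 3.5, SD 10, attrition 10% and power 0.80 come from Section 7.2. Two-sided alpha 0.05, the ±2.004 final boundary and its nominal two-sided level of 0.0456 come from Section 7.4. The paired analysis comes from Section 7.3. Assumption: 10 is the SD of the within-patient differences; the plan does not say. Below, benefit means the reduction in mYPAS score with VR, counted as positive.

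**Step 1: the plan's own figure.** Normal approximation: n = [10 × (1.960 + 0.842) / 3.5]² = 64.1, so 65. The exact paired t-test needs 67 completers, and 67 / 0.90 = 74.4, so 75 to recruit. That is within 2 of the stated 77, so the SD assumption fits the plan. With 69 completers (77 × 0.90 = 69.3, rounded down) power is 0.818.

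**Step 2: post hoc power at the observed effect.** With z = Φ⁻¹(1 − p/2), power = Φ(z − 1.96) + Φ(−z − 1.96), a function of p alone.

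| p | z | observed power |
|---|---|---|
| 0.05 | 1.960 | 0.50 |
| 0.10 | 1.645 | 0.38 |
| 0.20 | 1.282 | 0.25 |
| 0.50 | 0.674 | 0.10 |

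The noncentral t version gives the same values to two decimals and differs by no more than 0.001 between 69, 61 and 53 pairs.

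**Step 3: post hoc power at the planning values.** Noncentral t with noncentrality (3.5/10) × √n; n is 77 × (1 − attrition), rounded down.

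| attrition | pairs | power at 3.5, SD 10 |
|---|---|---|
| 10% | 69 | 0.818 |
| 20% | 61 | 0.767 |
| 30% | 53 | 0.706 |

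Allowing for the interim look gives 0.822, 0.774 and 0.714. These can be written down from the dropout count before any score is seen. A hybrid, 3.5 points with the observed SD, does use the data: at 61 pairs it gives 0.92, 0.77, 0.61 and 0.49 for SDs of 8, 10, 12 and 14. It still ignores the observed difference.

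**Step 4: the interval.** Half-width = t(0.975, n − 1) × 10/√n. The next column replaces 0.975 by 1 − 0.0456/2, as a simple approximation to the interim adjustment. The last column is 3.5 minus the unadjusted half-width.

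| pairs | half-width, unadjusted | half-width, final-stage level | 3.5 excluded if observed benefit is below |
|---|---|---|---|
| 69 | 2.40 | 2.45 | 1.10 |
| 61 | 2.56 | 2.61 | 0.94 |
| 53 | 2.76 | 2.81 | 0.74 |

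**Step 5: side by side at SD 10.**

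| pairs | p | benefit (95% CI, unadjusted) | observed power | power at 3.5 |
|---|---|---|---|---|
| 61 | 0.50 | 0.87 (−1.69 to 3.43) | 0.10 | 0.77 |
| 61 | 0.20 | 1.66 (−0.90 to 4.22) | 0.25 | 0.77 |
| 53 | 0.50 | 0.93 (−1.82 to 3.69) | 0.10 | 0.71 |

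The first row excludes 3.5, and still does at the final-stage level (0.87 + 2.61 = 3.48). The other two rows include both 0 and 3.5. Observed power is the same in rows one and three. Planning-value power is the same in rows one and two. Only the interval separates the informative result from the inconclusive ones.

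**Step 6: if 10 is the SD of a single score.** SD of differences = 10 × √(2(1 − ρ)): 14.1, 12.2, 10.0 and 7.1 at within-patient correlation 0, 0.25, 0.5 and 0.75. Half-widths scale in proportion. At 61 pairs the range is 2.56 × 1.414 = 3.62 (ρ = 0) to 2.56 × 0.707 = 1.81 (ρ = 0.75).

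**The case against.** The best defence is that the sentence follows directly on the design inputs and is triggered by a smaller n. The natural meaning may therefore be power at 3.5 points with the patients who remain. That stands as a possible reading. It rules out the sweeping inference that post hoc power can only restate the p-value, or must come out low: on this reading it is unrelated to p and falls only modestly. It does not rescue the sentence, because the figure describes the design and is silent on the result.

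Other inferences a reader might draw also go too far:

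- *That the plan offers only tests and no interval.* The mixed model in Section 7.3 estimates the treatment effect, and Section 7.4 names confidence limits. The gap is the missing commitment, the missing link to attrition and the missing comparison with 3.5.
- *That the plan will use post hoc power to explain away a null result.* Section 7.2 ties it to attrition, not to significance, and does not say how it will be interpreted.
- *That a half-width below 3.5 settles the matter.* To be sure of separating 0 from 3.5 it would have to be below 1.75. At 69 pairs an observed benefit between about 1.1 and 2.4 leaves both values inside the interval.
- *That 3.5 is a clinical threshold.* The documents give it only as the difference used for planning.

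**Conclusion.** The point holds in limited form: the plan's only stated response to attrition above 10% is left undefined, and on none of its possible readings does it show whether a non-significant result is compatible with the planned benefit. An interval shows this directly, although it too may be inconclusive.

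The consequence is moderate. No test, boundary or error rate changes, and the final decision still rests on ±2.004. What improves is the reading of a null result.

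The half-widths rest on 10 being the SD of the paired differences. The reproduced sample size supports that, but the plan does not state it; if 10 belongs to a single score and the within-patient correlation is below 0.5, the intervals are wider. An interval also measures lost precision only. If children leave because of VR discomfort, the remaining pairs may be a selected group, and neither an interval nor a power figure reveals that.

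**What to change.** Replace the last sentence of Section 7.2 with wording such as: *Whatever the attrition, the VR minus non-VR difference in mYPAS will be reported with its 95% confidence interval, adjusted for the interim look using the SEQTEST limits named in Section 7.4, and read against the planning difference of 3.5 points. The number of complete pairs will be stated. No post hoc power will be computed.*

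In Section 7.3, name the analysis that supplies the estimate. State the sign convention: under Section 7.4 a negative value is beneficial, so the reference value on the VR minus non-VR scale is −3.5. Say in Section 7.2 whether 10 is the SD of the differences or of a single score. Add a sentence on how patients with only one visit are handled, since the interval does not address bias from who drops out.

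The cost is a few sentences. No change to sample size, boundaries or data collection is needed, and the software procedure is already in the plan.

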7.3 Data Analyses

Categorical outcomes will be presented as frequency and percentages and compared using chi-square and/or Fisher's exact test. Continuous outcomes will be summarized by median and inter-quartile range (IQR) OR mean and standard deviation (depending on the data's distribution). Depending on the data's distribution a paired t-test or Wilcoxon-sign rank test will be performed to assess the difference between VR distraction and Non-VR distraction. For this crossover design a mixed model will also be implemented, which accounts for

treatment/intervention (VR vs. non-VR), sequence, and period as fixed effects. Patients will be nested within sequence.

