2.2 Secondary Objectives

2.2.1 Parents or legally authorized representative (LAR) subjective report decreased anxiety with the use of VR (secondary outcome).

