4.3 Follow-up Procedures

We will examine the CCBD schedule for the second opportunity to include each subject and complete the study in the other study arm (VR-distraction or Non-VR distraction). Surveys and Assessments will be filled out twice: once without the use of VR (control group) and the second time with the use of VR (study group).

Randomized Pilot Crossover Study Comparing Virtual Reality (VR) and Non-VR Distraction for Decreasing Preoperative/Procedural Anxiety as a Function of the modified Yale Preoperative Anxiety Scale (mYPAS)

Data collected will be compared and analyzed for statistically significant difference in anxiety scores with mYPAS. Parents' questionnaires will also be scored and evaluated for subjective improvement in parental assessment of preoperative anxiety.

All the study forms and questionnaires will be identified with the unique study ID number assigned in the study system with no other identifying data. There are no additional procedures outside the standard of care participants would normally receive. There will be no additional costs to subjects for participating in this study.

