We will then use the procedures of PROC SEQTEST in SAS to compare the obtained test statistic with these boundary values (at each stage) to evaluate the trial for stopping. For this two-sided symmetrical group sequential design, a standardized Z test statistic will be computed by standardizing the estimate of the effect in Preoperative Anxiety, and a negative Z test statistic indicates a beneficial effect. Thus, at the interim stage, if the standardized Z test statistic is less than or equal to the corresponding lower alpha boundary value, the null hypothesis is rejected for efficacy and the trial will be considered for stopping. Conversely, while not anticipated, if the standardized Z test statistic is greater than or equal to the corresponding upper alpha boundary value, the null hypothesis is rejected for a "harmful/safety" effect (exacerbated anxiety) and the trial will be considered for stopping. Otherwise, the process continues to the next stage. At the final stage (stage 2), the null hypothesis is rejected for efficacy if the Z statistic is less than or equal to the corresponding lower alpha boundary value of -2.004, and the null hypothesis is rejected for a "harmful/safety" effect if the Z statistic is greater than or equal to the corresponding upper alpha boundary value of 2.004. Otherwise, the null hypothesis is not rejected. When the trial is stopped at either the interim stage or at the final stage, the SEQTEST procedure can also be used to derive parameter estimates, confidence limits for the parameter, and p-values for hypothesis testing.

Figure 1.

Boundary Plot, which corresponds to the information in Table 1.

Note. Fixed Sample Design Critical Values ($\alpha=0.05$ two-sided): ± 1.96 .Note. Two planned stages: 1 interim stage at information fraction 0.67 ($n=52$) and a final stage ($N=77$).**Table 1.**Nominal Critical Values and Alpha Levels for a two-sided symmetrical group sequential design, with 2 stages, for Efficacy and Safety (O'Brien-Fleming, $\alpha=0.05$ two-sided, $\beta=0.20$)

Stage	Sample Size (N)	Nominal Critical Value (Z-value scale)	Nominal Alpha Level Lower	Nominal Alpha Level Upper	Nominal Alpha Level (two-sided)
1	52	± 2.431	0.00737	0.00737	0.01474
Final	77	± 2.004	0.02280	0.02280	0.04560

Note. Fixed Sample Design Critical Values ($\alpha=0.05$ two-sided): ± 1.96 .**Interim Analysis for Futility**

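### Section 7.3 names only chi-square and Fisher for categorical outcomes, so any categorical VR versus non-VR comparison in this crossover would ignore the pairing (minor, conditional)

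*Combined protocol and SAP*

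**What the plan says.** Section 7.1 sets out a two-period crossover with 1:1 randomization to the first mode: "During their second visit patients will be given the alternative mode of care". Section 4.3 confirms that each outcome is collected under both modes: "Surveys and Assessments will be filled out twice: once without the use of VR (control group", and a second time with VR.

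Section 7.3 then treats outcomes by type.
- Categorical: "Categorical outcomes will be presented as frequency and percentages and compared using chi-square and/or Fisher's exact test".
- Continuous: after a sentence on summaries, "Depending on the data's distribution a paired t-test or Wilcoxon-sign rank test will be performed to assess the difference between VR distraction and Non-VR distraction".
- In addition: "For this crossover design a mixed model will also be implemented", with treatment, sequence and period as fixed effects and patients nested within sequence. It is not tied to categorical data.

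The secondary objective in 2.2 is "Parents or legally authorized representative (LAR) subjective report decreased anxiety with the use of VR". Section 4.3 adds that the parents' "questionnaires will also be scored and evaluated for subjective improvement in parental assessment of preoperative anxiety". The questionnaire items (Appendices 10.2 and 10.3) are not in the supplied text, so their format is unknown here.

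**The concern.** Chi-square and Fisher's exact test assume independent observations. A child's VR and non-VR responses are not independent, because the same child is rated on both occasions. Section 7.3 respects the pairing for continuous data, but its only rule for categorical data is a rule for independent groups. An analyst who followed it for a categorical parent response, VR against non-VR, would use the wrong standard error.

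The direction depends on the within-child correlation. If it is positive, which is the natural expectation, the test is conservative and gives up the crossover's advantage, so a real difference in a parent-reported item could be missed. If it is negative, the test rejects too often.

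**Working it through.** **The plan's own figure.** Section 7.2 gives 77 patients for a difference of 3.5, SD 10, power 0.8 and 10% attrition. Alpha 0.05, two-sided, comes from 7.4. A paired t-test, with SD 10 read as the SD of within-child differences (7.2 does not say), needs 67 evaluable children. Then 67 / 0.90 = 74.4, or 75, within 2 of the stated 77. Two independent groups would need 129 per arm, or 144 after attrition. The stated size therefore fits a paired analysis. Completers: 77 × 0.90 = 69.3, so 69 pairs are used below.

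**Assumptions.** The documents give no categorical rates and no within-child correlation. Illustrative rates are 50% versus 33%, with phi varied.

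**False-positive rate.** With 50% in both modes, the true variance of the difference is (1 − phi) times the variance that chi-square uses. The actual size is therefore about 2 × [1 − Φ(1.96 / √(1 − phi))]:
- phi −0.2: 1.96 / 1.095 = 1.789, size 7.4% (simulated 7.3%)
- phi 0: 5.0%
- phi 0.2: 1.96 / 0.894 = 2.191, size 2.8% (simulated 2.8%)
- phi 0.5: 1.96 / 0.707 = 2.772, size 0.6% (simulated 0.6%)

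McNemar stays near 5% in the same simulations (0.048 to 0.055).

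**Power, worked at phi 0.2.**
- Covariance: 0.2 × √(0.50 × 0.50 × 0.33 × 0.67) = 0.2 × 0.2351 = 0.047.
- Positive under both modes: 0.50 × 0.33 + 0.047 = 0.212.
- Discordant cells: 0.50 − 0.212 = 0.288 and 0.33 − 0.212 = 0.118, total 0.406.
- True SE: √[(0.406 − 0.17²) / 69] = 0.0739.
- Chi-square null SE: √(2 × 0.415 × 0.585 / 69) = 0.0839. Power is about Φ[(0.17 − 1.96 × 0.0839) / 0.0739] = Φ(0.08) = 0.53.
- McNemar null SE: √(0.406 / 69) = 0.0767. Power is about Φ[(0.17 − 1.96 × 0.0767) / 0.0739] = Φ(0.27) = 0.61.

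Simulation (40,000 samples of 69 pairs, two-sided 0.05), which avoids the normal approximation, gives:

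| phi | chi-square | McNemar | mid-p McNemar |
|---|---|---|---|
| 0 | 0.52 | 0.53 | 0.51 |
| 0.1 | 0.52 | 0.57 | 0.55 |
| 0.2 | 0.52 | 0.63 | 0.60 |
| 0.3 | 0.53 | 0.69 | 0.66 |
| 0.5 | 0.53 | 0.83 | 0.82 |

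The pattern is similar at 30% versus 15%: chi-square 0.57 to 0.59, and McNemar 0.57, 0.62, 0.67, 0.72 and 0.86 over the same values of phi.

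**The case against.** The strongest reply is that the error has no confirmed target. The categorical sentence in 7.3 names no groups. The two sentences that do name VR against non-VR both use within-patient methods. Chi-square and Fisher are valid for comparing the two sequence groups, for example on the demographics form. Sections 2.1 to 2.3 name no categorical endpoint, and the questionnaires are to be scored. All of this stands, and it makes the point conditional and minor. It does not remove it: 7.3 states its rule for categorical outcomes in general and offers nothing else for a paired one.

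A second reply is that McNemar ignores period, just as the paired t-test does. That also stands, and the fix allows for it.

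Three stronger readings are tempting but unsupported.
- A reader might infer that the primary result is compromised. It is not: mYPAS is a numeric score, and 7.3 assigns it paired tests and a crossover model.
- A reader might infer that the parent report will be analysed by chi-square. The documents do not say so; scored questionnaires could fall under the paired tests.
- A reader might infer that the interim boundaries are at risk because 7.4 says only that "a standardized Z test statistic will be computed by standardizing the estimate of the effect in Preoperative Anxiety", without naming the analysis. That wording already excludes a signed-rank test. In simulation with no period effect, the paired t-test and the mixed model each give 5.1% false positives over both looks (5.2% if either may count) and equal power (0.811). Interim decisions differ in 1.1% to about 2.5% of trials for assumed period effects up to 2 points. This is missing detail, not an error.

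**Conclusion.** Minor, and wrong as written for any categorical VR versus non-VR comparison. It matters only if a parent-report item is analysed as categorical. At the assumed 50% versus 33% with 69 pairs, the power lost against McNemar is nil at phi 0, about 0.05 at phi 0.1, 0.10 at phi 0.2 and 0.30 at phi 0.5. With positive correlation the unpaired test adds no false positives; at phi −0.2 its size is about 7%. The rates and correlations are assumptions throughout. That the data are paired comes from the documents.

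**What to change.** In 7.3, state that any categorical VR versus non-VR comparison uses a matched method that allows for period: a period-adjusted matched test (Mainland-Gart or Prescott), or mixed logistic regression with treatment and period, in ordinal form for multi-level items. McNemar, in mid-p or exact form if discordant pairs are few, is the simple alternative when period is ignored. Keep chi-square and Fisher only for comparing the two sequence groups.

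The cost is wording; sample size, boundaries and data collection do not change. Some power may be lost if the correlation is zero or negative. At an assumed 60% versus 40%, McNemar has 0.65 against 0.66 for chi-square at phi 0, and 0.57 against 0.65 at phi −0.2, where chi-square exceeds its nominal size. The exact form can also lose at low correlation: at 50% versus 33% and phi 0.1, exact McNemar has 0.49 against 0.52 for chi-square and 0.45 for Fisher.

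Optional clarification: say in 7.4 that Z at both looks is the treatment estimate over its standard error from the mixed model already planned in 7.3.

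### Section 7.3 names no primary analysis and section 7.4 no source for its Z; if anxiety shifts between visits and sequences are near balance, the paired t-test has less power than the mixed model already planned

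*Combined protocol and SAP*

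**What the plan says.** Section 7.3 offers two tests of the within-child contrast, to be picked by the look of the data: "a paired t-test or Wilcoxon-sign rank test will be performed to assess the difference between VR distraction and Non-VR distraction". It gives no rule for the pick. It continues: "For this crossover design a mixed model will also be implemented". That model has fixed effects for treatment, sequence and period, with patients nested within sequence. No analysis is labelled primary in 7.3, and none is in section 2.1 or 4.3.

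Section 7.4 plans a look at 52 children and a final look at 77, with O'Brien-Fleming boundaries ±2.431 and ±2.004. Of the statistic to be compared with them it says only that "a standardized Z test statistic will be computed by standardizing the estimate of the effect in Preoperative Anxiety". If the lower interim boundary is crossed, "the null hypothesis is rejected for efficacy and the trial will be considered for stopping".

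Section 7.2 sets the size of the trial "to detect a difference of 3.5 in the mYPAS score; assuming a standard deviation of 10", with "a 10% reduction in patient participation due to attrition, and a power of 0.8". It does not say whether the SD belongs to a single visit or to the within-child difference. Section 7.1 describes sequence allocation as "1 to 1 randomization via Proc Plan in SAS 9.4" and does not mention blocking.

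**The concern.** Each look yields one verdict, and the text leaves open which of three analyses delivers it. They need not agree. Children may be more or less anxious at the second port access than at the first, whichever distraction they receive. The mixed model estimates that shift and removes it. The paired t-test and the signed-rank test do not, so it stays in their differences as noise when the sequences are balanced and as bias when they are not.

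At stake are the power of the primary test and a clear answer at the interim look if one analysis crosses the boundary and another does not.

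**Working it through.** **The plan's own figure.** Take SD 10 as the SD of the within-child difference (an assumption) and two-sided alpha 0.05 (from 7.4). The normal formula gives n = (10 × (1.960 + 0.842)/3.5)² ≈ 64.1, so 65 pairs, and 65/0.9 gives 73. The paired t-test needs 67 pairs, and 67/0.9 gives 75. The stated 77 is close to this. After 10% attrition 77 × 0.9 ≈ 69 children remain, and power is 0.818 for the paired t-test and 0.817 for the model if there is no shift.

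**How a shift enters.** Let D be VR minus non-VR and p the mean change from first to second visit. The mean of D is (effect − p) for VR-first children and (effect + p) for VR-second children. In a paired analysis:
- variance of D ≈ σ² + p² near balance, against σ² in the model;
- bias = p × (difference in completers between sequences)/n.

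**Power at the final test, 69 children, near balance.** The mean of D still varies with σ, but the paired t-test divides by the inflated SD. So power ≈ Φ(3.5√69/σ − 1.995 × √(σ² + p²)/σ). With σ = 10 (SD excludes the shift) this is Φ(2.907 − 1.995 × √(1 + p²/100)).

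| Shift p (assumed) | Formula | Paired t, simulated | Wilcoxon, simulated | Model, simulated |
|---|---|---|---|---|
| 2 | Φ(0.87) = 0.81 | 0.81 | 0.79 | 0.82 |
| 3.5 | Φ(0.79) = 0.79 | 0.785 | 0.76 | 0.82 |
| 5 | Φ(0.68) = 0.75 | 0.75 | 0.72 | 0.82 |
| 7 | Φ(0.47) = 0.68 | 0.68 | 0.64 | 0.82 |

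Simulated values average 35/34 and 34/35. Paired t falls below 0.80 at a shift somewhat above 2.5 points (0.801 at 2.5, 0.797 at 2.75). Its type I error at 35/34 is 0.045, 0.038, 0.029 and 0.017, which is conservative.

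**Two looks** (52 then 69 children, 2.431 and 2.004). The model has 0.82. Paired t has about 0.82, 0.80, 0.77 and 0.71 when the one-child imbalance works in its favour, and about 0.81, 0.79, 0.75 and 0.68 averaged over both directions.

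**If SD 10 already includes the shift,** σ² = 100 − p². Paired t has 0.82, 0.83, 0.85 and 0.89; the model has 0.83, 0.86, 0.91 and 0.98.

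**Unequal sequences.** At 37/32 with a 3.5-point shift the bias is 3.5 × 5/69 = 0.25 points. Paired t then rejects with probability about 0.84 or 0.72, depending on direction, against 0.82 for the model.

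**Interim look.** With 26/26, SD excluding the shift and estimate/SE against 2.431, the model crosses with probability 0.54 and paired t with about 0.52, 0.48, 0.43 and 0.34. They disagree in about 2%, 6%, 11% and 21% of trials. At exactly 26/26 with a shift of 2 points or more, paired t alone crosses in at most 0.2%; at 28/24 that rises to as much as 2.7%. These figures assume 52 complete pairs. With 10% attrition, 52 × 0.9 ≈ 47 pairs remain and the model's crossing probability is 0.49.

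**Raw estimate/SE as a Z.** Because the SD is estimated, comparing estimate/SE with ±2.431 and ±2.004 gives an overall type I error of about 0.054 to 0.056. Converting the t-based p-value to a Z brings it back to about 0.05 in simulation and lowers two-look power of the model from about 0.82 to 0.81.

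**The case against.** **A primary can be inferred.** The sample size reproduces roughly as a paired calculation, and the model is introduced as an addition, so paired test first and model supportive is a natural reading. The text does not say so. Even on that reading the choice between t-test and signed-rank test is left to the data, and the Z has no stated source.

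**The loss rests on an assumed shift.** This stands. The documents give none, and 7 points is twice the target difference. With two looks and a 3.5-point shift paired t is at about 0.79 to 0.80, so a material shortfall needs about 5 points or more, and then only if SD 10 excludes the shift.

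**The model is not always the more powerful test.** This also stands. With unequal completion, bias can raise the paired t rejection rate above the model's. That is not a merit, since the opposite direction lowers it by more. With heavy-tailed differences (t with 5 df, SD excluding the shift) the signed-rank test has 0.88 with no shift and 0.87, 0.84, 0.79 and 0.70 at the four shifts, against 0.82 for the model. It therefore wins at small shifts and loses at 5 points or more.

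**Stronger readings.** A reader might infer that the paired t-test inflates type I error. Near balance it is conservative. Eight losses from a 38/39 allocation can at worst leave 39/30, where its error is 0.050 to 0.054. A reader might also infer that an interim crossing forces a stop. Section 7.4 says only that stopping will be considered, although it does declare the null hypothesis rejected.

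**Conclusion.** The point holds in a conditional form. It is certain from the text that no primary analysis is named and that the Z has no stated source. Given normal differences and near-balanced sequences, the planned model is at least as powerful as the paired t-test, apart from one degree of freedom, under either reading of SD 10. The gain runs from nothing with no shift to about 7 percentage points at 5 points and 14 at 7 points (SD excluding the shift). With unequal sequences the argument for the model is freedom from bias, not power.

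The documents do not support saying that the trial is underpowered as written. That would need both a shift above about 2.5 points and an SD of 10 that excludes it, and neither is stated. The change is worth making before data are seen, because it settles which test decides and guards the stated 0.8 against a visit effect.

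**What to change.** In section 7.3, name the treatment contrast from the planned mixed model (treatment, period and sequence fixed; patient within sequence random) as the single primary analysis. In section 7.4, state that this contrast and its standard error give the Z at both looks, with the t-based p-value converted to a Z before comparison with ±2.431 and ±2.004.

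Keep the paired t-test and a rank test as sensitivity analyses that do not decide the primary hypothesis. The better rank test is a rank-sum comparison, between sequences, of first-minus-second-visit differences. It removes the shift and has power 0.88 at every shift in the heavy-tailed case above.

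The cost is wording in two sections, one degree of freedom (0.817 against 0.818 with no shift), about one percentage point of power for the conversion, and some power lost to a rank test if the differences are heavy-tailed and the shift is small. Naming the model does not settle which mYPAS observation from section 4.2 enters it, or how children with one visit are handled; the same edit should state both.
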